6.2.3.1 Hemolytic Anemia

When there are clinical symptoms and/or laboratory signs of hemolytic anemia, dosing should be discontinued. Clinical symptoms are described in Section 7.1.3.1 and laboratory signs are described in Section 7.3.2. Follow-up laboratory monitoring is also

⁵ Administrative reasons (or other reasons not related to safety) are not to be considered safety reasons warranting treatment discontinuation.

described in Section 7.3.2. The medical monitor should be contacted to discuss whether or not resumption of dosing is indicated or for any other questions.

6.2.3.2 *Serotonin Syndrome*

Subjects are to be monitored at each visit by a medically qualified person for signs and symptoms indicative of potential serotonin toxicity, especially when initiating LMTM in this study or any medication with serotonergic potential. At each post-Baseline visit, subjects are to be evaluated by targeted physical and neurological examination and measurement of temperature, respiratory rate, blood pressure, and pulse (see Section 7.1.3.2 for guidance on assessment). Should serotonin syndrome (toxicity) be suspected clinically, treatment should be immediately discontinued. The event should be reported as an AESI and the medical monitor should be contacted for further guidance on subject management.

6.2.3.3 *Other Safety Reasons Requiring Dose Adjustment*

Treatment should be discontinued if the following treatment-emergent change occurs on ECG (based on the means of the three recordings) without other explanatory cause:

- QTcF interval > 500 msec: repeat ECGs should be obtained, in triplicate, within 2 weeks; if confirmed by the mean of the repeat ECGs, study drug should be discontinued pending further evaluation.

Other clinically significant changes in the ECG should be discussed with the medical monitor.

If renal concerns arise and the calculated creatinine clearance is < 30 mL/min, study drug should be discontinued.

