7.1.3.1 Hemolytic Anemia

The subject should be evaluated at each visit for possible clinical symptoms associated with hemolytic anemia, in conjunction with review of hematology results. Should hemolytic anemia be suspected, follow-up testing should be performed as described in Section 7.3.2. The medical monitor should be contacted to discuss whether or not resumption of dosing is indicated or for any other questions.

The signs and symptoms of anemia include:

- Cyanosis, headache, anxiety, exercise intolerance, fatigue, confusion, dizziness, tachypnea, palpitation, dysrhythmia, seizures, and coma

Signs of possible hemolytic anemia include:

- Decrease by 20% from Baseline in RBC count and/or hemoglobin
- Abnormal RBCs in peripheral blood smear
- Elevation of reticulocyte count to above laboratory normal range
- Increase in LDH or indirect bilirubin, or low haptoglobin

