7.3.1 Serum Chemistry

The blood volume for each chemistry panel will be approximately 3.5 mL. Blood samples collected for serum chemistry panels are to be destroyed approximately 1 week after testing has been completed. The chemistry panel will include the following analytes:

Sodium	Gamma-glutamyl transpeptidase (GGT)
Potassium	Alanine transaminase (ALT)
Calcium	Aspartate transaminase (AST)
Albumin	Glucose (random, not fasted)
Total protein	Creatinine ²
Urea nitrogen, urea ¹	Phosphorus
Total and direct (conjugated) bilirubin (indirect bilirubin calculated as the difference)	Uric acid
Alkaline phosphatase	Chloride
Lactate dehydrogenase (LDH)	Creatine kinase (CK)

¹ The analytical method measures urea in serum. In the Covance CLS database, the test is named either Urea Nitrogen or Urea, depending on whether the results are expressed in conventional or SI units, respectively. Urea Nitrogen is reported in mg/dL while Urea is reported in mmol/L per SI unit convention.

² Creatinine clearance is to be estimated by the central laboratory using the Cockcroft-Gault equation.

7.3.2 *Hematology*

The blood volume for each hematology panel will be approximately 2.0 mL. Blood samples collected for hematology panels are to be destroyed approximately 3 days after testing has been completed. The hematology panel will include the following analytes:

Hematocrit	White blood cells (WBC)
Hemoglobin	and absolute and percent differential
Mean corpuscular hemoglobin (MCH)	(neutrophils, lymphocytes, monocytes, eosinophils, basophils); any abnormal cells
Mean corpuscular hemoglobin concentration (MCHC)	will be noted
Red blood cells (RBC) and any immature forms	Platelet count
RBC morphology	Mean cell volume (MCV)
Reticulocyte count and percent	

If the investigator is concerned on the basis of significant hematological abnormalities that Heinz bodies may be present, a blood sample may be sent to the local laboratory for assessment and screening of Heinz bodies. The percent of erythrocytes with Heinz bodies should be reported based on a suitably prepared slide; blood samples should be as fresh as possible at the time of slide preparation. If Heinz bodies are present, study medication must be stopped (see Section 6.2.3.1) and another blood sample should be obtained within 1 week. Hematological indices should continue to be monitored until this resolves.

7.3.3 *Other Laboratory Tests*

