9.6.2 Laboratory Tests

Descriptive statistics will be based on central laboratory results as described below. Laboratory results that are obtained from laboratories other than the central laboratory will not be included in tabular summaries. They will, however, be listed separately. Normal ranges will be provided by the central laboratory and each local laboratory used for testing parameters other than Heinz bodies.

Categorical laboratory parameters will be summarized for each target visit using counts and percent of subjects in each result category. Continuous laboratory parameters will be summarized for each target visit using descriptive statistics for both the original values and the change from Baseline. For each analyte, Baseline values will be restricted to those subjects in the Safety Population for whom there is at least one post-Baseline value.

Selected parameters for which normal ranges differ may additionally be summarized by gender, age, and country (or region).

Box and whisker plots will be presented for selected parameters including hemoglobin, reticulocytes, neutrophils, and liver function tests.

Shift tables will be provided cross tabulating the number of subjects who are low, normal, or high at Baseline (with respect to the normal range) against results at each target week.

Potentially clinically significant ranges will be defined in the SAP for selected parameters, and the number and percent of subjects meeting these criteria summarized. Tabular summaries will be based on those subjects who meet criteria at Baseline and those in whom the values represent a treatment-emergent worsening.

Listings of laboratory parameters will be presented. Listings will flag results above and below the normal range as well as those that meet criteria for being potentially clinically significant (whether or not a treatment-emergent worsening). Separate listings for each hematology and chemistry parameter will show results that meet criteria for being potentially clinically significant. In addition, for subjects who have one or more result that meets criteria, all laboratory results will be displayed.

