Thresholds for potentially clinically significant (PCS) laboratory abnormalities are defined in [Appendix B](#) for selected parameters. When there are thresholds provided for low and high values, they will be handled separately. Summaries will include the number and percent of subjects with treatment-emergent PCS values, restricted to those subjects in

whom the values represent a post-baseline worsening (PCST); the number meeting criteria at baseline will also be summarized. A PCST is defined as any PCS event that happened at any post-baseline visit and has a value more out of range than the value for a particular test at baseline (see [Appendix D](#) for directionality of worsening).

Listings of laboratory parameter results will be presented. Listings will include all laboratory flags provided by the central laboratory in the data transfer as well as flags for those that meet criteria for being PCS (whether or not a study-emergent worsening); additionally, results evaluated by the investigator as abnormal/clinically significant will be flagged in the listing. A separate listing for samples that could not be analyzed and the corresponding comments will be provided.

Separate listings for each hematology and chemistry parameter will include only subjects with treatment-emergent PCS values and, for these subjects, all laboratory results for the parameter meeting PCS criteria and related parameters (e.g., ALT, AST, bilirubin, neutrophils, WBC, etc.) will be provided.

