**Appendix B: Criteria for Determining Potentially Clinically Significant Values in Laboratory Test Results**

Test	Criteria	
	System International Units	Conventional Units
Hemoglobin	Female: $\leq 95$ g/L; Male: $\leq 115$ g/L Decrease of $\geq 20\%$	Female: $\leq 9.5$ g/dL; Male: $\leq 11.5$ g/dL
Hematocrit	Female: $\leq 0.32$ ; Male: $\leq 0.37$	Female: $\leq 32\%$ ; Male: $\leq 37\%$
WBC count	$\leq 2.8 \times 10^9/L$ $\geq 16 \times 10^9/L$	$\leq 2800/\mu L$ or $\geq 16000/\mu L$
Neutrophils	$\leq 1.0 \times 10^9/L$	$\leq 1000/\mu L$
Eosinophils	$\geq 0.7 \times 10^9/L$	$\geq 700/\mu L$
Platelet count	$\leq 75 \times 10^9/L$ $\geq 700 \times 10^9/L$	$\leq 75 \times 10^3/\mu L$ $\geq 700 \times 10^3/\mu L$
Sodium	$<130$ mmol/L $>150$ mmol/L	$<130$ mEq/L $>150$ mEq/L
Potassium	$< 3.0$ mmol/L $> 5.5$ mmol/L	$< 3.0$ mEq/L $> 5.5$ mEq/L
Calcium	$< 1.75$ mmol/L $> 3.00$ mmol/L	$< 7.00$ mg/dL $> 12.00$ mg/dL
Glucose, fasting/nonfasting/unknown	$< 2.775$ mmol/L $>13.875$ mmol/L	$< 50$ mg/dL $> 250$ mg/dL
Uric acid	Female: $>475.8$ $\mu\text{mol/L}$ ; Male: $>594.8$ $\mu\text{mol/L}$	Female: $> 8$ mg/dL; Male: $>10$ mg/dL
Albumin	$<25$ g/L	$<2.5$ g/dL
Total bilirubin	$\geq 34.2$ $\mu\text{mol/L}$	$\geq 2$ mg/dL
ALT	$\geq 3 \times \text{ULN}$	$\geq 3 \times \text{ULN}$
AST	$\geq 3 \times \text{ULN}$	$\geq 3 \times \text{ULN}$
Alkaline phosphatase	$\geq 3 \times \text{ULN}$	$\geq 3 \times \text{ULN}$
Urea (nitrogen)	$> 17.85$ mmol/L	$> 50$ mg/dL
Creatinine	$\geq 177$ $\mu\text{mol/L}$	$\geq 2$ mg/dL
CK	$\geq 3 \times \text{ULN}$	$\geq 3 \times \text{ULN}$
GGT	$\geq 3 \times \text{ULN}$	$\geq 3 \times \text{ULN}$
LDH	$\geq 3 \times \text{ULN}$	$\geq 3 \times \text{ULN}$
Phosphorus	$< 0.646$ mmol/L $> 1.777$ mmol/L	Low: $<2.0$ mg/dL High: $>5.5$ mg/dL

ULN = Upper Limit of Normal

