path\l\_program.sas date time

*Programming note: Sort by subject ID. Display the CRF visit label.*

*Repeat this listing for:*

*Listing 16.2.8.5.2 Hematology Results of Potential Clinical Significance - SI Units (Safety Population)*

*Listing 16.2.8.5.3 Hematology Results of Potential Clinical Significance - Includes Only Hgb and Hct reticulocyt (Safety Population): If either RBC or Hgb meets PCS for any visit, then both labs values for all visits will be required in format of Listing 16.2.6.2.1.*

*Listing 16.2.8.5.4 Hematology Results of Potential Clinical Significance - WBCs and Neutrophils (Safety Population): If either parameter meets PCS for any visit, then the values for all visits are required, in format of Listing 16.2.6.2.1*

*Listing 16.2.8.5.5 Hematology Results of Potential Clinical Significance – Eosinophils (Safety Population)*

*Listing 16.2.8.5.6 Hematology Results of Potential Clinical Significance – Platelets (Safety Population)*

*Listing 16.2.8.6.1 Serum Chemistry Results of Potential Clinical Significance – Conventional Units (Safety Population)*

*Listing 16.2.8.6.2 Serum Chemistry Results of Potential Clinical Significance – SI Units (Safety Population)*

*Listing 16.2.8.6.3 Serum Chemistry Results of Potential Clinical Significance - Urea (Nitrogen) or Creatinine (Safety Population): If either parameter meets PCS for any visit, then Urea (Nitrogen), Creatinine, plus Creatinine Clearance and eGFR are required for all visits, in format of Listing 16.2.6.3.1*

*Listing 16.2.8.6.4 Serum Chemistry Results of Potential Clinical Significance - ALT, AST, GGT, bilirubin, alkaline phosphatase (Safety Population): If any of one of these parameters meets PCS, display the results for all 4 parameters.*

**Listing 16.2.9.1  
Vital Signs  
Safety Population**

Subject ID	Visit	Date of Measurement (Study Day)	Time of Measurement	Temperature (°C)	Temperature Method	SBP (mmHg)	DBP (mmHg)	Pulse (beats/min)	Weight (kg)	Any Findings Abnormal?
xxxxxx	Baseline	date9. (xx)	time5.	xx.x.	xxx.x	xx.x	xx	xxx	xxx	Yes: CS/NCS / No
	Week 2	date9. (xx)	time5.		xxx.x	xx.x	xx	xxx	xxx	Yes: CS/NCS / No
	Week 13	date9. (xx)	time5.		xxx.x	xx.x	xx	xxx	xxx	Yes: CS/NCS / No
xxxxxx	...									
	Baseline	date9. (xx)	time5.	xx.x.	xxx.x	xx.x	xx	xxx	xxx	Yes: CS/NCS / No
	Week 2	date9. (xx)	time5.		xxx.x	xx.x	xx	xxx	xxx	Yes: CS/NCS / No
xxxxxx	Week 13	date9. (xx)	time5.		xxx.x	xx.x	xx	xxx	xxx	Yes: CS/NCS / No
	...									

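### SAP Appendix B has no criterion for creatinine clearance or red cell count, so the laboratory values the protocol names for each are not counted, and one listing selects on a red cell criterion that does not exist

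*Protocol*

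**What the plan says.** **Protocol.** Section 6.2.3.3 gives a two-part renal rule: study drug should be stopped where there are renal concerns and the "calculated creatinine clearance is < 30 mL/min". Section 7.3.1 says where the value comes from: "Creatinine clearance is to be estimated by the central laboratory using the Cockcroft-Gault equation". Among the signs of possible haemolytic anaemia, Section 7.1.3.1 lists "Decrease by 20% from Baseline in RBC count and/or hemoglobin". Section 9.6.2 leaves the choice of limits to the analysis plan: "Potentially clinically significant ranges will be defined in the SAP for selected parameters".

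**SAP.** Section 7.2 states "Thresholds for potentially clinically significant (PCS) laboratory abnormalities are defined in" Appendix B, headed "Criteria for Determining Potentially Clinically Significant Values in Laboratory Test Results". Its renal rows are creatinine (2 mg/dL or more) and urea nitrogen (above 50 mg/dL). Its red cell rows are haemoglobin (absolute limits by sex and a 20% decrease) and haematocrit (absolute limits by sex). Creatinine clearance, eGFR and red cell count have no row.

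Two listing notes in Appendix I depend on Appendix B:
- Listing 16.2.8.5.3 has a title naming haemoglobin and haematocrit, but its note reads "If either RBC or Hgb meets PCS for any visit, then both labs values for all visits will be required".
- Listing 16.2.8.6.3 shows creatinine clearance and eGFR only for subjects whose urea or creatinine has met PCS.

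**The concern.** Evaluating long-term safety and tolerability is among the study's primary objectives. Table 14.3.3.3.1 is where a reader would look for how many subjects reached a laboratory value of concern. The protocol itself names two such values, clearance below 30 mL/min and a 20% fall in red cell count, and neither can appear there. For clearance, the nearest rows use different analytes, so a subject can be below 30 mL/min without being flagged. Such a subject also stays out of the renal PCS listing, because that listing opens only on urea or creatinine. For red cell count, a listing rule refers to a criterion that was never written, so a programmer must either ignore it or guess what was meant.

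**Working it through.** **Side-by-side check**

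| Protocol laboratory value | SAP limit or category | Worsening direction in Appendix D |
|---|---|---|
| Creatinine clearance < 30 mL/min (6.2.3.3) | none | lowest value |
| Red cell count down 20% (7.1.3.1) | none | lowest value |
| Haemoglobin down 20% (7.1.3.1) | present in Appendix B | lowest value |
| QTcF > 500 msec (6.2.3.3) | counted in SAP 7.5 and Table 14.3.4.5.3 | highest value |

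For the two missing items the direction of worsening is already set and only the threshold is absent. The other numeric value in Protocol 6.2.3.3, QTcF, does get a count.

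**Can the creatinine row stand in for clearance?** The documents name Cockcroft-Gault but do not print it. The usual form is

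CrCl = (140 − age) × kg × (0.85 if female) / (72 × creatinine in mg/dL).

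The creatinine at which CrCl equals 30 is therefore (140 − age) × kg × (0.85 if female) / 2160. At the PCS limit of 2.0 mg/dL, CrCl is the same numerator divided by 144. The two units of the PCS limit agree: 2 × 88.4 = 176.8, against 177 µmol/L. The ages and weights below are assumptions, because the documents give no distribution.

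| Subject | Numerator | Creatinine at CrCl 30 (mg/dL) | CrCl at creatinine 2.0 (mL/min) |
|---|---|---|---|
| Woman 80 y, 60 kg | 60 × 60 × 0.85 = 3060 | 1.42 | 21.25 |
| Woman 75 y, 60 kg | 65 × 60 × 0.85 = 3315 | 1.53 | 23.0 |
| Woman 75 y, 70 kg | 65 × 70 × 0.85 = 3867.5 | 1.79 | 26.9 |
| Man 80 y, 70 kg | 60 × 70 = 4200 | 1.94 | 29.2 |
| Woman 65 y, 80 kg | 75 × 80 × 0.85 = 5100 | 2.36 | 35.4 |
| Man 75 y, 80 kg | 65 × 80 = 5200 | 2.41 | 36.1 |

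In the first four rows a subject can be below 30 mL/min with creatinine under 2. In the last two the creatinine limit is reached first. Setting the crossover to 2.0 gives kg = 4320 / [(140 − age) × (0.85 if female)]. Below that weight the creatinine row is the later one: 72.6, 78.2 and 84.7 kg for women of 70, 75 and 80 years, and 61.7, 66.5 and 72.0 kg for men.

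**How many?** This cannot be derived from the documents. Illustrative simulations used one creatinine value per subject, mean age 70 or 75, mean weight 60 to 72 kg for women and 72 to 85 kg for men, and several assumed creatinine distributions. The share of subjects below 30 mL/min whose creatinine was under 2 ran from about 19% to nearly 100%. Against the anticipated 1050 to 1400 subjects, that is from about 1 (1050 × 0.0010 × 0.994) to about 90 (1400 × 0.0719 × 0.895). The urea row was not modelled and would lower these figures. A range this wide shows only that the number is unknown.

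**Red cell count.** The haemoglobin half of the sign is covered. What escapes the 20% criterion is a red cell fall of 20% with a smaller haemoglobin fall. Mean corpuscular haemoglobin is haemoglobin divided by red cell count, so this happens when that index has risen. The documents give no basis for its frequency.

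**Listing 16.2.8.5.3.** The red cell part of the selector can never be true. Haematocrit has a criterion and is in the title, but it is not in the selector, so a subject with only haematocrit meeting PCS is not selected for this listing. The rule needs repair whichever analyte was meant.

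**The case against.** The protocol delegates PCS limits to the SAP for selected parameters, and nothing requires those limits to reproduce the protocol's action values. The SAP nowhere offers creatinine as a substitute for clearance. The data are also not lost. Clearance falls within the by-visit chemistry summaries, which show minimum values, and is listed for every subject in Listing 16.2.8.3.1. Red cell count is in the haematology tables and listings. Urea gives a second route into the renal listing, and Listings 16.2.8.5.1 and 16.2.8.5.2 cover haematology PCS results generally. All of this stands, and it limits the point to a missing flag, a missing count and faulty listing selection.

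A reader might infer more, and the documents do not support it:

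- *That the creatinine row misses many subjects, or most women between 20 and 30 mL/min.* No age, weight or creatinine distribution is given. A woman of 75 years and 70 kg is flagged at every clearance up to 26.9.
- *That haemolytic anaemia is undercounted as an event of special interest.* Those events are recorded as adverse events (Protocol 7.1.3) and tabulated from adverse event data (SAP 7.1, Tables 14.3.2.14.x). Appendix B does not touch them.
- *That a count of clearance below 30 would be a count of stopping events.* The protocol rule also requires that renal concerns have arisen, which a laboratory table cannot show.
- *That a 20% red cell fall is itself a stopping value.* Section 7.1.3.1 lists it as a sign of possible haemolytic anaemia, with follow-up testing if the condition is suspected.

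Discretion over parameters does not answer the listing note, which calls on a criterion the SAP does not contain.

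**Conclusion.** The point holds in a limited form. Appendix B omits creatinine clearance and red cell count, so Table 14.3.3.3.1 gives no count for either protocol value. It is an absent count, not a falsely low one. The creatinine and urea rows can miss subjects below 30 mL/min, mainly older or lighter ones, while in younger or heavier subjects the creatinine row fires first. This rests on the standard Cockcroft-Gault form and on assumed ages and weights, and the number affected is unknown. The Listing 16.2.8.5.3 selector is wrong as written, and that needs no assumption. The change is worth making because long-term safety is among the primary objectives and the correction is nearly free.

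**What to change.** 1. Add two rows to Appendix B: creatinine clearance below 30 mL/min, using the central laboratory value, and red cell count decreased by 20% or more from baseline, worded like the existing haemoglobin row. Label both as laboratory reporting flags that mirror protocol values, not as stopping events.
2. Carry both rows into Table 14.3.3.3.1 and its repeat for non-AChEI/memantine users, and let the clearance flag open Listing 16.2.8.6.3 alongside urea and creatinine.
3. Reconcile the Listing 16.2.8.5.3 note with its title and Appendix B, so that it selects on haemoglobin, haematocrit and, once defined, red cell count. The same notes cite Listings 16.2.6.2.1 and 16.2.6.3.1 for format. The first is the EQ-5D-5L listing and the second is not in the list of listings, so both references need correcting.

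The cost is two appendix rows and some edited programming notes. The data are already collected, Appendix D already gives the direction of worsening, and no clinical rule changes.

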6.3 Packaging, Labeling, and Storage

The open-label study drug will be packaged, labeled, and distributed to study sites by a designated vendor.

Study drug supplied to subjects will be packaged in 35-count 60-mL white HDPE bottles containing a 2-g desiccant bag and induction-sealed. The number of bottles dispensed is to be adequate to ensure sufficient supplies until the next scheduled study visit (with 2-week overage).

Study drug package labels will be in compliance with applicable regulatory requirements and will include the statement “Keep out of reach of children”, the cautionary statement “Caution: New Drug – Limited by Federal (United States) law to investigational use” and/or “For clinical trial use only” as appropriate, as well as any other locally mandated statements. Labels will also be translated into the local language.

At a minimum, labels will also include the following information: the name and address of the sponsor, the study code, a unique identifier, and appropriate contact information. In those jurisdictions where required, a re-test or expiry date will be included.

At the study site, study drug must be stored securely (*e.g.*, locked area, pharmacy) and at a temperature not more than 30°C. The temperature at which study drug is stored at the study site will be recorded daily using a centralized temperature monitoring system if this

is available. If not, study drug storage temperature will be recorded each working day using a maximum-minimum thermometer. While closed, the packaging protects the study drug from light and moisture; study drug should be ingested immediately after removal from the package.

Subjects and caregivers should also be provided with information about required storage conditions. Study drug should remain in the package as dispensed until it is ingested by the subject, and should not be placed in an alternate pill box including commonly-used weekly pill organizers.

